### 6.2.3.1. Laboratory Values

Haematology				
Laboratory Parameter	Units	Category	Clinical Concern Range	
			Low Flag (< x)	High Flag (>x)
Hematocrit	Ratio of 1	Male		0.54
		Female		0.54
		Change from Baseline	Decrease of 0.075	
Haemoglobin	g/L	Male	75	180
		Female	75	180
		Change from Baseline	Decrease of 25	
Lymphocytes	x10  / L		0.8	
Neutrophil Count	x10  / L		1.5	
Platelet Count	x10  / L		100	550
Red blood cell (RBC) count	million/mcL		4.2	6.1
Mean corpuscular volume (MCV)	fl.		80	100
Mean corpuscular hemoglobin (MCH)	picograms (pg)		27.5	33.2
%Reticulocytes	%		0.5	2
Monocytes	%		2	8
Eosinophils	%		1	4
Basophils	%		0.5	1
Clinical Chemistry				
Laboratory Parameter	Units	Category	Clinical Concern Range	
			Low Flag (< x)	High Flag (>x)
Calcium	mmol/L		2	2.75
Creatinine	%	Change from Baseline		Increase of 30%
Glucose	mmol/L		3	11
Potassium	mmol/L		3	5.5
Sodium	mmol/L		130	150
Direct bilirubin	mg/dl		<0.3	<0.3
Total protein	g/dl		6	8.3
Blood urea nitrogen (BUN)/Urea	mg/dl		5	20

Haematology				
Laboratory Parameter	Units	Category	Clinical Concern Range	
			Low Flag (< x)	High Flag (>x)
Creatine phosphokinase (CPK)	mcg/l		10	120
Homocysteine	µmol/L		4	14
Antiphospholipid antibodies	MPL		0	39.9
Sex hormone binding globulin (SHBG)	nmol/L		18	144

Liver Function				
Test Analyte	Units	Category	Clinical Concern Range	
ALT	IU/L	High	$\geq 3x$ ULN	
AST	IU/L	High	$\geq 3x$ ULN	
T Bilirubin	µmol/L	High	$\geq 1.5x$ ULN	

ULN = Upper Limit of Normal; ALT=Alanine Aminotransferase; AST=Aspartate Aminotransferase;

T. Bilirubin=Total Bilirubin

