**Table 3 Objectives and Endpoints**

Objective(s)	Endpoint(s)
Primary	
To assess the effect of steady state exposure of GSK3036656 on the single dose PK of EE and LNG in healthy female participants of non-childbearing potential	Area under the plasma concentration-time curve to infinity AUC(0-inf) and maximum observed concentration (C max ), after a single dose of EE and LNG (EE AUC (0-inf) , EE C max , LNG AUC (0-inf) , LNG C max )
Secondary	
To characterize the steady state PK of GSK3036656 in the presence of EE/LNG	AUC(0- $\tau$ ), C max , C t (Day 8, 10, 12, 15 and 16) and time of maximum observed concentration (T max ) for GSK3036656
To characterize the single dose PK of EE/LNG alone and in the presence of GSK3036656	AUC(0-t), T max and t 1/2 for EE and LNG, in Treatment Period 1 and Treatment Period 3.
To assess the safety and tolerability of GSK3036656 and Microgynon when given alone or in combination in healthy female participants of non-childbearing potential	
 
• Incidence of SAEs within each treatment period.
 
• Incidence of AEs of grade 3 severity or higher within each treatment period.
 
• Incidence of AEs considered by the investigator to be possibly, probably, or definitely related to study drug within each treatment period (overall and separately for relationship to Microgynon and to GSK3036656).
 
• Incidence of participants withdrawn from the treatment/study due to adverse events within each treatment period.
 

Objective(s)	Endpoint(s)
	
 
Incidence of ECG values PCI within each treatment period.
 
Incidence of clinical chemistry laboratory values of PCI within each treatment period.
 
Incidence of hematology laboratory values of PCI within each treatment period.
 
Incidence of vital signs parameters of systolic blood pressure (SBP), diastolic blood pressure (DBP) and heart rate (HR) of PCI within each treatment period.
 

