#### 9.3.4.1. Main Analytical Approach

All safety analyses will be performed on the Safety Population. Safety data will be presented in tabular format by treatment groups (Microgynon, GSK3036656 and Microgynon+GSK3036656) and summarized descriptively according to GSK's Integrated Data Standards Library standards. For each treatment group, the denominator for percentages (N) will be the number of participants entering the associated treatment period. No formal statistical analysis of the safety data will be conducted. The values of PCI for laboratory parameters, ECGs and vital signs will be detailed in the SAP.

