#### ***4.3.2.2.3. *Clinical Laboratory Values****

The haematology and clinical chemistry laboratory data, relative to PCI criteria, will be summarized by treatment group, laboratory test and category.

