#### **4.4.1. Additional Safety Assessments**

##### **4.4.1.1. Laboratory Data**

In addition to laboratory summaries related to PCI criteria, summaries of worst-case grade increase from baseline will be provided for all the lab tests that are gradable by CTCAE v4.03. These summaries will display the number and percentage of subjects with a maximum post-baseline grade increasing from their baseline grade. Any increase in grade from baseline will be summarized along with any increase to a maximum grade of 3 and any increase to a maximum grade of 4. Missing baseline grade will be assumed as grade 0. For laboratory tests that are graded for both low and high values, summaries will be done separately and labelled by direction, e.g., sodium will be summarized as hyponatremia and hypernatremia separately.

Change from period baseline values of haematology and chemistry will be summarized using descriptive statistics.

For lab tests that are not gradable by CTCAE v4.03, summaries of worst-case changes from baseline with respect to normal range will be generated. Decreases to low, changes to normal or no changes from baseline, and increases to high will be summarized for the worst-case post-baseline. If a subject has a decrease to low and an increase to high during the same time interval, then the subject is counted in both the “Decrease to Low” categories and the “Increase to High” categories.

Separate summary tables for haematology and chemistry laboratory tests will be produced. Liver function laboratory tests will be included with chemistry lab tests.

Protocol-required routine urinalysis tests will also be summarized descriptively.

An e-DISH plot of maximum post baseline total bilirubin versus maximum post baseline ALT will be created.

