### 6.2.4. Study Period

Assessments and events will be classified according to the time of occurrence relative to the study intervention period.

Treatment period 1 ranges from Day 1 dose to Day 4 predose, similarly treatment period 2 ranges from Day 4 dose to Day 15 predose and treatment period 3 ranges from Day 15 dose until Day 18.

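### The SAP's PCI limits for direct bilirubin give the same entry, <0.3 mg/dl, as both the low and the high flag, so the row needs correcting (minor)

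*SAP*

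**What the plan says.** Protocol 9.3.4.1 leaves the PCI limits to the SAP: "The values of PCI for laboratory parameters, ECGs and vital signs will be detailed in the SAP". They matter because Protocol Table 3, repeated in SAP Table 1, lists as a secondary safety endpoint "Incidence of clinical chemistry laboratory values of PCI within each treatment period". SAP 4.3.2.2.3 then says that the haematology and chemistry data, "relative to PCI criteria, will be summarized by treatment group, laboratory test and category". SAP 6.2.3 makes the tables that follow it the source of the flags.

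In the chemistry block of SAP 6.2.3.1 the row is "Direct bilirubin mg/dl <0.3 <0.3". The first entry stands in the low-flag column, whose heading means below x. The second stands in the high-flag column, whose heading means above x. Direct bilirubin is one of the required chemistry tests in Protocol Table 10, so the row will be used.

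**The concern.** A high flag that carries a less-than sign and repeats the low limit cannot be what was meant. Whoever programs the table must either follow the cell, follow the column heading, or substitute a limit that is not in the plan. The first two give a misleading row, and the third is an undocumented choice made after the SAP was approved. The protocol also uses the direct fraction of bilirubin in its liver rules, so a reader of the study report may well look at this row.

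**Working it through.** **Inputs.** From SAP 6.2.3.1: the entry <0.3 mg/dl in both columns; column signs of below x for low and above x for high. From the Protocol Schedule of Activities: laboratory tests at Screening and on Days 1, 4, 15 and 18. From SAP 6.2.4: the period boundaries. From Protocol 9.5: approximately 20 participants. There is no sample size or power figure to reproduce; the check is to apply the rule.

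**Step 1. Apply the row under each reading.** Let v be the result in mg/dl.

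- Reading A, cell as printed: low if v < 0.3; high if v < 0.3.
- Reading B, column signs with x = 0.3: low if v < 0.3; high if v > 0.3.

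| v (mg/dl) | Reading A | Reading B |
|---|---|---|
| 0.1 | low and high | low |
| 0.2 | low and high | low |
| 0.3 | none | none |
| 0.5 | none | high |
| 2.0 | none | high |

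Reading A marks low results as high and never marks a raised one. Reading B marks raised results, but leaves nothing unflagged except a result of exactly 0.3.

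**Step 2. Compare with the other rows.** The other 19 two-sided rows in the haematology and chemistry blocks all have a low limit below the high limit, for example calcium 2 and 2.75, potassium 3 and 5.5, total protein 6 and 8.3. Direct bilirubin is the only row with the same entry in both columns, and the only one whose numbers carry their own sign.

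**Step 3. Look for the intended limit elsewhere.** The total bilirubin flag (1.5 x ULN) is for a different analyte. Exclusion criterion 6 and the liver rules in Protocol 10.3.2 and 10.4 use direct bilirubin as a percentage (35%), not as a concentration. SAP 6.2.3 says that the laboratory supplies reference ranges, but neither document prints one for this test. The intended limits cannot be recovered from the documents.

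**Step 4. Count the results that the row classifies.** SAP 6.2.4 says "Treatment period 1 ranges from Day 1 dose to Day 4 predose"; period 2 runs to the Day 15 predose point and period 3 to Day 18. Each period therefore holds one scheduled post-dose laboratory result: Day 4, Day 15 and Day 18. The total is 20 x 3 = 60 at most. This counts results passed through the rule, not expected misclassifications, which depend on a distribution of values that the documents do not give.

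**The case against.** The strongest reply is that the column headings govern, so Reading A is a misreading and raised values would be flagged after all. That is a fair reading of the table and removes the worst consequence. It does not rescue the row, because the low flag at the same number remains.

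Second, display detail is deferred to the Output and Programming Specification, which is not among the documents and may already hold a correction. This makes the harm conditional but leaves the SAP entry wrong.

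Third, the entry could be a fault of PDF reading. That cannot be fully excluded, but the neighbouring rows read cleanly.

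Fourth, other displays show liver abnormalities: the total bilirubin, ALT and AST flags, the e-DISH plot and the CTCAE grade shifts. SAP 4.4.1.1 adds that "For lab tests that are not gradable by CTCAE v4.03, summaries of worst-case changes from baseline with respect to normal range will be generated". This stands in full and limits the consequence, although none of these displays repairs the direct bilirubin row.

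Last, the documents do not show which of the two cells is mistaken. Other rows carry both a low and a high limit (homocysteine 4 and 14, basophils 0.5 and 1), so the low flag cannot simply be declared superfluous. This also stands, and the remedy has to leave the choice open.

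**Conclusion.** The row is wrong as written, and the error is minor. The finding assumes only that the row in the SAP is as it reads here. The effect is confined to one analyte in a descriptive secondary safety table. The primary PK analysis does not use it.

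Three stronger inferences are tempting and are not supported:

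- **That raised liver values would go unseen in this trial.** The other displays remain, and the liver stopping rule does not depend on this row.
- **That the haemoglobin limits are also in error.** The SAP flags values below 75 g/L or a "Decrease of 25" g/L from the period baseline, while Protocol 7.1.3 stops at below 8.0 g/dL, that is 80 g/L. No passage requires PCI limits to contain stopping limits, and the two serve different purposes. Stopping calls for confirmation on a second sample within 24 hours, or investigator discretion. Stopping criteria are a recorded reason for discontinuation (Protocol 7.1), and those reasons are summarised (SAP 6.1.1).
- **That resetting the baseline on Days 4 and 15 is a mistake because it does not test cumulative change.** The endpoints are defined within each treatment period, and the baseline rule matches them. A listing of cumulative change would be an optional extra.

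**What to change.** Before database lock, correct the direct bilirubin row in SAP 6.2.3.1. State a valid high limit, to be applied with the sign in the column heading. Then either delete the low flag or state a valid low limit that is distinct from the high limit and below it. The sponsor must supply the numbers. Carry the same entry into the Output and Programming Specification.

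The cost is one corrected table row, with no new data and no burden on participants.

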## **10.2. Appendix 2: Clinical laboratory tests**

- The tests detailed in [Table 10](#) will be performed by the local laboratory.
- Protocol-specific requirements for inclusion or exclusion of participants are detailed in Section [5](#) of the protocol.
- Additional tests may be performed at any time during the study as determined necessary by the investigator or required by local regulations.
- Investigators must document their review of each laboratory safety report.

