**Table 10 Protocol-required safety laboratory tests**

Laboratory Tests	Parameters
Haematology	Platelet count Red blood cell (RBC) count RBC indices: Mean corpuscular volume (MCV) Mean corpuscular hemoglobin (MCH) Hemoglobin Hematocrit %Reticulocytes WBC count with differential: Neutrophils Lymphocytes Monocytes Eosinophils Basophils
Clinical chemistry	Aspartate aminotransferase (AST)/serum glutamic-oxaloacetic transaminase (SGOT) Alanine aminotransferase (ALT)/serum glutamic-pyruvic transaminase (SGPT) Alkaline phosphatase  Total bilirubin Direct bilirubin Total protein Blood urea nitrogen (BUN)/Urea Potassium Creatinine* Sodium Calcium Glucose [indicate if fasting or nonfasting] Creatine phosphokinase (CPK) Homocysteine Antiphospholipid antibodies Sex hormone binding globulin (SHBG)
Routine urinalysis	Specific gravity pH, glucose, protein, blood, ketones, [bilirubin, urobilinogen, nitrite, leukocyte esterase] by dipstick Microscopic examination (if blood or protein is abnormal) Epithelial cells Red Blood cells WBC Casts Crystals Culture (if positive: specify pathogen)
Pregnancy testing	Highly sensitive [serum or urine] human chorionic gonadotropin (hCG) pregnancy test (as needed for WOCBP) 

Laboratory Tests	Parameters
Other screening tests	Follicle stimulating hormone and estradiol (as needed in WONCBP only) [Serum or urine] [alcohol and drug screen (to include at minimum: amphetamines, barbiturates, cocaine, cotinine, opiates, cannabinoids and benzodiazepines)] [Serology [(HIV antibody 4th generation test, HBsAg, and HCV antibody)] SHBG

NOTES:

1. Details of liver chemistry stopping criteria and required actions and follow-up are given in Section 7.1.1 :Liver Chemistry Stopping Criteria and Section 10.4: Liver Safety: Suggested Actions and Follow-up Assessments [and Study Intervention Rechallenge Guidelines]]. All events of ALT [or AST]  $\geq 3 \times$  ULN and total bilirubin  $\geq 2 \times$  ULN ( $> 35\%$  direct bilirubin) or ALT [or AST]  $\geq 3 \times$  ULN and INR  $> 1.5$  (if INR measured), which may indicate severe liver injury (possible Hy's law), must be reported to [sponsor] in 24 hours (excluding studies of hepatic impairment or cirrhosis).
2. If alkaline phosphatase is elevated, consider fractionating.
3. Local urine testing will be standard for the protocol unless serum testing is required by local regulation or IRB/IEC

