**Table 1: Objectives, Estimands and Endpoints**

Objectives	Endpoints
Primary	

 
• To assess the effect of steady state exposure of GSK3036656 on the single dose PK of EE and LNG in healthy female participants of non-childbearing potential
 
	
 
• Area under the plasma concentration-time curve to infinity <math>AUC_{(0-\infty)}</math> and maximum observed concentration (<math>C_{max}</math>), after a single dose of EE and LNG (EE <math>AUC_{(0-\infty)}</math>, EE <math>C_{max}</math>, LNG <math>AUC_{(0-\infty)}</math>, LNG <math>C_{max}</math>)
 

Secondary	

 
• To characterize the steady state PK of GSK3036656 in the presence of EE/LNG
 
• To characterize the single dose PK of EE/LNG alone and in the presence of GSK3036656
 
• To assess the safety and tolerability of GSK3036656 and Microgynon when given alone or in combination in healthy female participants of non-childbearing potential
 
	
 
• <math>AUC_{(0-\tau)}</math>, <math>C_{max}</math>, <math>C_\tau</math> (Day 8, 10, 12, 15 and 16) and time of maximum observed concentration (<math>T_{max}</math>) for GSK3036656
 
• <math>AUC_{(0-t)}</math>, <math>T_{max}</math> and <math>t_{1/2}</math> for EE and LNG, in Treatment Period 1 and Treatment Period 3.
 
• Incidence of SAEs within each treatment period.
 
• Incidence of AEs of grade 3 severity or higher within each treatment period.
 
• Incidence of AEs considered by the investigator to be possibly, probably, or definitely related to study drug within each treatment period (overall and separately for relationship to Microgynon and to GSK3036656).
 
• Incidence of participants withdrawn from the treatment/study due to adverse events within each treatment period.
 
• Incidence of ECG values of PCI within each treatment period.
 

Objectives	Endpoints
	
 
• Incidence of clinical chemistry laboratory values of PCI within each treatment period.
 
• Incidence of hematology laboratory values of PCI within each treatment period.
 
• Incidence of vital signs parameters of systolic blood pressure (SBP), diastolic blood pressure (DBP) and heart rate (HR) of PCI within each treatment period.
 

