### 6.2.3. Criteria for Potential Clinical Importance

Reference ranges for all laboratory parameters collected throughout the study are provided by the laboratory. A laboratory value that is outside the reference range is considered either high abnormal (value above the upper limit of the reference range) or low abnormal (value below the lower limit of the reference range). Note: a high abnormal or low abnormal laboratory value is not necessarily of clinical concern.

National Cancer Institute Common Terminology Criteria for Adverse Events [NCI-CTCAE v4.0.3] will be used to assign grades to the relevant laboratory parameters, blood pressure and QTc.

In addition, the following criteria will be used to flag potential clinical importance (for laboratory data, ECG parameters and vital signs):

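### SAP 6.2.3.1 sets one PCI limit (below 5 or above 20 mg/dl) for both BUN and urea, which differ 2.14-fold, and states the CPK limit in a mass unit: a minor ambiguity in a descriptive safety endpoint

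*SAP*

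**What the plan says.** SAP 6.2.3 introduces fixed thresholds and states that "the following criteria will be used to flag potential clinical importance". In the clinical chemistry part of 6.2.3.1, one row is labelled "Blood urea nitrogen (BUN)/Urea", with unit mg/dl, a low flag at 5 and a high flag at 20. The row that follows, beginning "Creatine phosphokinase (CPK", has unit mcg/l, a low flag at 10 and a high flag at 120. The liver function part of the same section gives ALT and AST in IU/L, with limits set as multiples of ULN.

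Protocol Appendix 2 (10.2) says that the safety tests "will be performed by the local laboratory". Its Table 10 lists the tests by name only, as in "Blood urea nitrogen (BUN)/Urea Potassium Creatinine". It gives no units and does not say whether BUN or urea will be reported. SAP 6.2.3 adds that "Reference ranges for all laboratory parameters collected throughout the study are provided by the laboratory", but the BUN/urea and CPK rows use fixed numbers rather than those ranges.

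The rows feed a secondary safety endpoint in SAP Table 1: "Incidence of clinical chemistry laboratory values of PCI within each treatment period". Protocol 9.3.4.1 leaves the PCI values to the SAP, so this table is the operative definition.

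**The concern.** BUN and urea are two ways of expressing the same substance. BUN counts only the mass of the nitrogen, and urea counts the whole molecule. A limit in mg/dl that is right for one is therefore wrong for the other by a fixed factor, and the row does not say which it means.

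Units elsewhere in the table are mixed. Calcium, glucose, potassium and sodium are in mmol/L and total bilirubin is in µmol/L, while direct bilirubin is in mg/dl and total protein in g/dl. If the laboratory reports urea in mmol/L, a programmer has to convert it, and the SAP gives no factor. Converting as urea or as urea nitrogen would both follow the text.

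For CPK, a mass limit has no stated link to a result reported as enzyme activity. The only way to use the row on such a result would be to apply 120 to a different quantity.

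What is at stake is whether two entries in a pre-specified incidence table have a single defined meaning before the data are seen.

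**Working it through.** The PCI limits are fixed thresholds, so the plan contains no calculation to reproduce. The check converts the limits under each reading and then asks how many healthy values each reading would flag.

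**Inputs**
- Limits 5 and 20 mg/dl, from SAP 6.2.3.1.
- Molar mass of urea 60.056 g/mol and of its two nitrogen atoms 2 × 14.007 = 28.014 g/mol. These come from atomic masses, not from the documents.
- Distribution of BUN in healthy women: not in the documents, so assumed. The base case treats 5–20 mg/dl as the central 95% range for BUN. The sensitivity grid takes means of 8–16 and SDs of 3–5 mg/dl, normal shape.

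**Step 1, ratio.** 60.056/28.014 = 2.144.

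**Step 2, limits under each reading.** mmol/L = (mg/dl × 10)/molar mass.

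| Reading of the row | Low limit | High limit | Equivalent in the other quantity |
|---|---|---|---|
| BUN | 50/28.014 = 1.78 mmol/L | 200/28.014 = 7.14 mmol/L | urea 5 × 2.144 = 10.7 and 20 × 2.144 = 42.9 mg/dl |
| Urea | 50/60.056 = 0.83 mmol/L | 200/60.056 = 3.33 mmol/L | BUN 5/2.144 = 2.3 and 20/2.144 = 9.3 mg/dl |

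**Step 3, base case.** Mean 12.5, SD 15/(2 × 1.96) = 3.83 mg/dl BUN.
- Read as BUN: 5% flagged, low and high together. This follows from the assumption and is not evidence for it.
- Read as urea, high flag: 1 − Φ((9.33 − 12.5)/3.83) = 0.80.
- Read as urea, log-normal with the same 95% range: log mean ln 10, log SD ln 4/3.92 = 0.354, so 1 − Φ((ln 9.33 − ln 10)/0.354) = 0.58.

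SAP 6.2.4 and the Schedule of Activities give one scheduled post-dose chemistry sample per treatment period (Day 4 predose, Day 15 predose, Day 18). The share of samples is therefore roughly the share of participants: 0.58 × 20 ≈ 12 to 0.80 × 20 = 16 of 20 women on the urea reading, against 0.05 × 20 = 1 on the BUN reading.

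**Step 4, sensitivity grid.** Each cell gives the share flagged high if read as urea / the share flagged low or high if read as BUN.

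| Mean BUN (mg/dl) | SD 3 | SD 4 | SD 5 |
|---|---|---|---|
| 8 | 33% / 16% | 37% / 23% | 40% / 28% |
| 10 | 59% / 5% | 57% / 11% | 55% / 18% |
| 12 | 81% / 1% | 75% / 6% | 70% / 14% |
| 14 | 94% / 2% | 88% / 8% | 83% / 15% |
| 16 | 99% / 9% | 95% / 16% | 91% / 23% |

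The ranges are about 33%–99% for urea and 1%–28% for BUN. The urea share passes 50% once mean BUN exceeds 9.3 mg/dl. The 28% corner is almost all low flags: Φ((5 − 8)/5) = 27.4% low, and 1 − Φ((20 − 8)/5) = 0.8% high.

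**Step 5, CPK.** The SAP legend identifies the comparison rows: "ALT=Alanine Aminotransferase; AST=Aspartate Aminotransferase". All three tests are enzymes. Two are in activity units with limits tied to ULN, and CPK is in mass units with fixed limits. Neither document gives the laboratory's CPK unit, a conversion factor or a distribution, so no flag rate can be calculated.

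**The case against.** The strongest reply is that the row works as it stands if read as BUN. BUN is named first, the row sits near other conventional-unit entries such as direct bilirubin and total protein, and under the base assumption only about 5% of values are flagged. Nothing in the documents says that the laboratory will report urea. All of that stands, and it makes the over-flagging conditional. It does not settle the text: the label covers both quantities, Table 10 repeats it without units, and no conversion is given. SAP 4.1.1 defers further detail to the Output and Programming Specification, which may settle the units but is not available here.

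Three stronger readings should be resisted.
- A reader might infer that most healthy women will be flagged. That needs the urea reading and a distribution that the documents do not supply; at an assumed mean of 8 mg/dl the share is 33%–40%.
- A reader might infer that the CPK row cannot be used or will flag most women. Neither is shown, because the laboratory's unit is not stated and a mass result would fit the row.
- A reader might infer that a noisy row would hide a renal signal for a drug that Protocol Table 2 describes as mainly renally cleared. The SAP does not support this. Creatinine has its own PCI row (a 30% increase from baseline), PCI results are summarised test by test, and SAP 4.4.1.1 plans change-from-baseline summaries, CTCAE grade shifts and normal-range shifts. Protocol 8.3.4 also requires the investigator to review laboratory results and record clinically significant changes.

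The consequences are also small. Safety is summarised descriptively with no formal testing, and the QTc, haematology and liver stopping criteria (Protocol 7.1.2, 7.1.3 and Appendix 4) do not use BUN, urea or CPK.

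**Conclusion.** The point holds as a minor one. One 5–20 mg/dl limit cannot be right for both BUN and urea: the 2.14 factor is exact and moves the high limit between 7.14 and 3.33 mmol/L. How much this matters depends on what the local laboratory reports and how a result is converted, which the documents leave open. The flagged shares of 33%–99% (urea) and 1%–28% (BUN) rest wholly on the assumed means, SDs and normal shape, and show direction and order of size rather than a forecast. For CPK, the finding is only a unit mismatch with the other enzymes in the section: the limit does not apply directly if the laboratory reports activity. The effect is confined to the descriptive chemistry PCI incidence. The primary PK analysis and the sample size are unaffected.

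**What to change.** Before database freeze, amend two rows of SAP 6.2.3.1.

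1. **BUN/urea.** Confirm with the local laboratory which quantity and unit it reports, and name the analyte to which 5–20 mg/dl applies. If BUN is the intent, add the equivalent urea limits of 10.7–42.9 mg/dl (1.8–7.1 mmol/L) and state the conversion: urea = 2.144 × BUN in mg/dl; mmol/L = BUN in mg/dl × 10/28.014.
2. **CPK.** Restate the limit in the unit that the laboratory reports, or as a multiple of the laboratory ULN in the manner of ALT and AST. The multiple is for the sponsor to specify.

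The cost is a short SAP edit and the matching programming specification. It needs no new data, no change to the schedule and no extra burden on participants.
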